4 GENERAL STATISTICAL METHODS

4.1 Analysis Sets

4.1.1 Intent-To-Treat Population (ITT)

All enrolled (consented) subjects for whom TraceIT administration is attempted. This will be the primary analysis population for evaluation of feasibility (i.e., technical success defined as the ability to place TraceIT and create space between the duodenum and HOP).

4.1.2 Modified Intent-To-Treat Population (MITT)

All subjects enrolled in the study and who are a Technical Success will be included in the Modified Intent-to-Treat population. This will be the primary analysis population for purposes of non-safety outcome data.

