6.4.5.2 Post-Injection CT Scan Acquisition

Following the TraceIT hydrogel injection, each subject is to undergo a repeat planning simulation scan to obtain a second RT radiation computer treatment plan with the TraceIT Tissue Spacer *in situ*.

The first and second RT treatment plans (pre- and post-TraceIT Tissue Spacer injection) will be compared to evaluate the displacing properties of the TraceIT Tissue Spacer.

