3 ENDPOINT ANALYSIS

All data collected in this study will be documented using summary tables and subject data listings. Continuous variables will be summarized using descriptive statistics, specifically the mean, median, standard deviation, minimum and maximum, when appropriate.

Categorical variables will be summarized by frequencies and percentages.

Changes from baseline in dosimetric parameters and quality of life parameters will be assessed using a paired t-test or, if not normally distributed, the nonparametric Wilcoxon Signed-Rank test for continuous variables and Chi-Square and/or McNemar's test for dichotomous variables.

Nominal p-values associated with statistical tests will be reported, but no significance level will be applied to the values. No adjustments to nominal p-values are planned since this is a hypothesis-generating study.

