3.1.1 Hypotheses

This is an early feasibility study with an intent to collect information on the procedural characteristics and safety for TraceIT administration within the peri-duodenal space. Therefore, no formal hypothesis tests of primary or secondary effectiveness endpoints have been planned.

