3.1.2 Sample Size

No formal hypothesis or sample size estimation has been established since this is an early feasibility study with an intent to collect information concerning the procedural characteristics and safety for TraceIT administration within the peri-duodenal space. Six (6) subjects should provide sufficient experience to allow for evaluation of procedural safety and to estimate the impact of space creation on duodenal radiation doses.

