3.2.1 Statistical Methods

Radiotherapy Benefits will be assessed via comparison RT planning performed at baseline and post-TraceIT administration for MITT and PP population. For both scans, summary descriptive statistics will be presented by assessment (i.e., Pre- vs. Post-TraceIT Administration) for all target volume and dose constraint measurements. The GTV/PTV receiving prescription dose pre- and post-TraceIT will be reported in an additional table. For the post-TraceIT procedure data, the relative reduction from baseline in dose (V15, V20, V35, mean and maximum duodenal dose, etc.) to the duodenum will also be calculated and summarized.

For continuous radiotherapy benefit variables, the paired sample t-test will be used to test for a difference in means between treatment plans.

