3.3.1 Statistical Methods

The proportion of resected subjects in the MITT or PP population, localized (resectable, BRPC or LAPC) subgroup may be calculated with an exact (Clopper-Pearson) 95% confidence interval for the true proportion, when appropriate.

The incidence of acute (within 3 months) and late (>3 months) duodenal toxicity for unresected subjects will be reported by CTCAE grade and timing.

Histology of duodenal tissue (Duodenum Damage Score) will be summarized for those subjects when resection is performed.

The summary of theoretical dose escalation from post-TraceIT treatment plan, and , migration and stability at 2-6 weeks post-TraceIT, TraceIT persistence at 6-months post-TraceIT in non-resected subjects will be presented in separated table. The pre-TraceIT and post-TraceIT duodenal space measured by site during index procedure and/or by independent assessors will be summarized separately. Average duodenal space will be

calculated if the measurements were taken from multiple observation points or duplication.

The EORTC QLQ-C30 is a questionnaire developed to assess the quality of life of cancer patients. The pancreatic cancer module QLQ-PAN26 is intended for patients at all disease stages undergoing surgical resection, palliative surgical intervention, endoscopic palliation or palliative chemotherapy. Changes in Quality of Life Measures as assessed overall and subdomains (scales) of the EORTC-QLQ-C30 and QLQ-PAN26 will be evaluated.

The five functional scales (physical, role, emotional, cognitive and social), three symptom scales (fatigue, nausea & vomiting and pain), a global health status/QOL scale, and six single items (dyspnea, insomnia, appetite loss, constipation, diarrhea and financial difficulties) from EORTC-QLQ-C30 will be summarized according EORTC QLQ-C30 Scoring Manual third edition.

The fifteen symptom items and two functional scales from QLQ-PAN26 will be analyzed according EORTC QLQ-PAN26 Scoring Manual 2.2.

Those analysis will be repeated by localized (resectable, BRPC and LAPC), as well as resected and unresected subgroup, if applicable. Scores will be compared to baseline using either a paired t-test or Wilcoxon Signed-Rank test when appropriate.

The result of comparability of visualization of the fiducial marker and TraceIT hydrogel will be summarized using a standardized visualization score for all subjects injected with TraceIT Tissue Spacer.

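### The pre/post dose comparison is planned only in Technical Successes, although every injected subject is scheduled for a second plan, so the summarised dose benefit is conditional on technical success

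*SAP*

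**What the plan says.** SAP 4.1.2 (and Protocol 7.3.2 in the same terms) builds the MITT set on the technical result: "All subjects enrolled in the study and who are a Technical Success will be included in the Modified Intent-to-Treat population". It then gives that set its role: "This will be the primary analysis population for purposes of non-safety outcome data". The PP set (SAP 4.1.3) is MITT without major deviations, so it also contains only Technical Successes.

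For the secondary effectiveness endpoint, SAP 3.2.1 states: "Radiotherapy Benefits will be assessed via comparison RT planning performed at baseline and post-TraceIT administration for MITT and PP population". No ITT or all-injected version is planned.

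The protocol collects the paired dosimetry more widely. Section 6.4.5.2 says: "Following the TraceIT hydrogel injection, each subject is to undergo a repeat planning simulation scan". Section 6.4.6 calls for planning studies before and after injection in every subject, and Section 5 says treatment follows the post-injection plan. None of these is conditional on Technical Success. Only subjects in whom no gel could be injected are excused further imaging (Protocol 6.4.5.1 and 6.4.7).

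Resection incidence is tied to the same sets in SAP 3.3.1: "The proportion of resected subjects in the MITT or PP population". That section names no population for quality of life, PFS or OS, so these fall to MITT by default.

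**The concern.** Technical Success under SAP 3.1 is read from the post-injection CT, so entry to the dose analysis depends on something observed after the injection. The protocol schedules paired plans for an injected subject who fails the criterion, but the planned summary leaves them out.

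The study objective is to evaluate radiotherapy benefit when the spacer is used. A mean among successes answers a narrower question: how much dose falls given that placement succeeded. Someone who wants to know what happened to duodenal dose across everyone injected gets no summarised answer. In a study of six, leaving out one subject can move the mean noticeably.

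**Working it through.** **1. Is there a plan figure to reproduce?** No. SAP 3.1.2 gives six subjects without a formal calculation: "Six (6) subjects should provide sufficient experience to allow for evaluation of procedural safety". SAP 3.1.1 adds that "no formal hypothesis tests of primary or secondary effectiveness endpoints have been planned". There is no alpha, power, effect size or SD. The figures below are illustrations on stated assumptions.

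**2. Who is in each set?**

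| Subject | Second plan scheduled? | In MITT/PP dose summary? |
|---|---|---|
| Injected, Technical Success | Yes | Yes (PP if no major deviation) |
| Injected, not a Technical Success | Yes | No |
| Attempted, nothing injected | No | No |

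The middle row is the gap. SAP 4.1.4 foresees it, because it lists absence of created space as a failure separate from abandoned placement. It assigns no analysis to that No TraceIT set.

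**3. How far can the two means differ?** Let n subjects be injected and have two plans, k of them Technical Successes with mean reduction R. Assume no change in failures. Then:

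all-injected mean = (k × R + (n − k) × 0) / n = (k/n) × R

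With n = 6, each failure removes one sixth of the MITT mean. R is assumed:

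| R in successes | 6/6 | 5/6 | 4/6 |
|---|---|---|---|
| 30% | 30% | 25.0% | 20.0% |
| 40% | 40% | 33.3% | 26.7% |
| 50% | 50% | 41.7% | 33.3% |

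For example, (5 × 40% + 0)/6 = 33.3% and (4 × 40% + 0)/6 = 26.7%. If failures gain something, the gap is smaller; if they gain as much as successes, there is none.

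**4. How does the gap compare with the precision?** Constructed data with mean 50% and SD 20% in successes (both assumed), no change in failures, and t intervals:

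| Successes | MITT mean (95% CI) | All six (95% CI) |
|---|---|---|
| 5/6 | 50.0% (25.2 to 74.8) | 41.7% (13.2 to 70.2) |
| 4/6 | 50.0% (18.2 to 81.8) | 33.3% (1.7 to 64.9) |

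The intervals overlap heavily. What differs is the quantity being estimated and the headline figure.

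**5. How likely is any failure?** P(at least one in six) = 1 − p⁶ for a true success rate p (assumed): 26% at 95%, 47% at 90%, 74% at 80%, 88% at 70%. Some failures could be non-injections, which have no second plan and which an all-injected set would not recover.

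**6. Which definition decides exclusion?** SAP 3.1 needs gel between pancreas and duodenum with visibility score 2 or higher, and score 2 is the faint or trace grade in Protocol 6.4.8. It does not require space. SAP 4.1.1 describes Technical Success as placement plus space creation, and SAP 4.1.4 treats absence of space as failure. A subject with visible gel and no space would be in MITT under SAP 3.1 and also in the No TraceIT set under SAP 4.1.4. The protocol has the same split between 6.1.2 and 7.3.1 on one side and 7.6.2 on the other.

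**The case against.** The strongest reply is that the conditional estimate is partly intended. SAP 3.1.2 says six subjects should allow an estimate of the effect of space creation on duodenal dose, and that quantity presupposes space. The success rate is reported separately in ITT with an exact interval (SAP 3.1.3), so a reader can see how often placement worked and what followed when it did. This stands as a reason to keep MITT. It does not fully justify having only MITT and PP, because under SAP 3.1 MITT does not isolate subjects in whom space was created.

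Second, the study is descriptive: "Nominal p-values associated with statistical tests will be reported, but no significance level will be applied to the values". No error rate is at stake. SAP 3 also promises subject listings, so an injected failure's two plans should be visible if collected. Both points limit the severity, but neither supplies a summarised all-injected result.

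Third, a reader might infer that all non-safety outcomes are confined to Technical Successes. The SAP does not support that. Technical Success is analysed in ITT (3.1) and visibility in all injected subjects (3.3.1). Concomitant medication, examination and laboratory summaries use ITT (5.1.5 to 5.1.7). Baseline data and medical history are shown for ITT as well as MITT and PP (5.1.2, 5.1.3). MITT is called the primary set, not the sole one.

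Fourth, an all-injected set is itself selected, since it omits attempted but non-injected subjects. A partly injected subject whose placement was abandoned might also never reach a planning CT. That is why the proposed set is limited to injected subjects with two plans and the number left out should be stated.

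**Conclusion.** The point holds for the dose comparison. SAP 3.2.1 restricts it to sets defined by a post-injection result, while the protocol schedules paired plans for all injected subjects. Resection incidence shares the restriction, and quality of life, PFS and OS share it by default.

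If six are injected and failures show no change, the MITT mean overstates the all-injected mean by one sixth of its value per failure: 40% against 33% with one failure, 40% against 27% with two. The 40%, the number of failures and the zero change are all assumptions. If all six succeed, the analyses coincide.

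A reader might infer that the plan necessarily inflates the benefit. The documents support only the weaker statement that the MITT figure will be higher if failures gain less, which is plausible but not established. Nor do they require the all-injected result to displace MITT as the primary set fixed in Protocol 7.3.2; that would be a choice of estimand, and it is not needed here. The point is a worthwhile, inexpensive improvement to a descriptive feasibility study.

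**What to change.** In SAP 3.2.1:

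- Add the same pre/post dosimetry summary for all injected subjects with two plans, alongside MITT and PP. SAP 3.3.1 already uses an all-injected group for visibility scores, so the set has a precedent.
- Label the MITT and PP dose results as conditional on Technical Success.
- State that attempted but non-injected subjects have no scheduled second plan, and print their number beside the result.

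In SAP 3.1, 4.1.1 and 4.1.4, and in the matching protocol sections, reconcile the visibility-based and space-based definitions of Technical Success, because they decide who is excluded.

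The cost is one extra table from data already scheduled for collection, plus a wording change. The downside is that the all-injected reduction may be smaller than the MITT figure.

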4.1.3 Per-Protocol Population (PP)

The Per Protocol (PP) Population is defined to be all subjects in the MITT population with no major protocol deviations that have the potential to affect the study outcomes.

Major protocol deviations will be defined by the clinical project manager.

4.1.4 No TraceIT Population

Subjects who were enrolled (consented) and for whom TraceIT administration was not technically successful (either hydrogel placement was abandoned due to clinical issues or no space created in the duodenal/pancreatic interface).

4.1.5 Safety Population (SAF)

The Safety Population is defined to be all subjects for whom TraceIT administration is attempted (whether or not administration was successful). For the purposes of this study, the Safety Population is the same as the ITT Population.

4.2 Control of Systematic Error/Bias

All practical monitoring and follow-up steps will be taken to ensure complete and accurate data collection.

4.3 Number of Subjects per Investigative Site

About 6 people will be in this study at up to 4 clinics site in the United States. There is no limitation for number of subjects in each site.

5 ADDITIONAL DATA ANALYSES

5.1 Other Endpoints/Measurements

5.1.1 Subject Disposition

The number and percentage of ITT, MITT, PP and SAF population will be summarized. Subjects who passed pre-screening will be consented for the study and will undergo a secondary screening. The number of subjects who consented, screening failed and early terminated prior index procedure (TraceIT administration isn't attempted) will be presented. The number and percentage of non-injection TraceIT subjects will be presented along with the reason they were not able to be injected. The number and percentage of treated subjects who do not complete the study will be presented, along with the reason for early termination/withdrawal. Subject accountability by investigative site and by study visit will also be presented.

5.1.2 Demographics and Baseline Characteristics

Subjects will be summarized with respect to baseline demographics and clinical characteristics (e.g., age, sex, tumor grade, resection status etc.) by ITT, MITT and PP population. These will be summarized by descriptive statistics including means, medians,

standard deviations and ranges (for quantitative variables) and percentages (for categorical variables).

5.1.3 Medical History

Medical history will be summarized by status (resolved and ongoing) for ITT, MITT and PP population. Tumor and therapy related medical history will be summarized in separated table.

The tumor anatomic stage will be calculated using the algorithm according Protocol REV.C Appendix A AJCC PANCREAS CANCER STAGING.

Anatomic Stage/Prognostic Groups			
Stage 0	Tis	N0	M0
Stage IA	T1	N0	M0
Stage IB	T2	N0	M0
Stage IIA	T3	N0	M0
Stage IIB	T1	N1	M0
	T2	N1	M0
	T3	N1	M0
Stage III	T4	Any N	M0
Stage IV	Any T	Any N	M1

5.1.4 Study Procedure

The index procedure will be summarized with number of fiducial markers placed, duration of EUS (time between EUS insertion and removal), duration of fiducial insertion (time between first and last fiducial insertion), duration of TraceIT needle (time between TraceIT needle insertion and removal), duration of TraceIT injection (time between TraceIT injection start and stop), the number of TraceIT injections, total volume of TraceIT used. Numbers and percentages of subjects given prophylactic antibiotics prior to procedure, whether TraceIT injection procedure successful, ease of access to injection site who experienced any access difficulties, any device malfunction, and feedback of device ease of use, ease of preparation will be presented.

A listing will include index procedure date, EUS insertion and removal time, first and last fiducial insertion time, fiducial placement success, type of fiducial, number of fiducial markers, TraceIT needle insertion and removal time, needle type, TraceIT injection start and stop time, FNA needle gauge usage and dilution factor, total volume of TraceIT, pre- and post-TraceIT space measurement, number of injections, device malfunction, access difficulties and description, prep ease, ease of use and any AEs during index procedure.

5.1.5 Concomitant Medication

Numbers and percentages of subjects in the ITT population with any medication changes to treat intestinal symptoms will be summarized by the timing of start administration.

The timing of concomitant medication will be categorized as prior index procedure date, from index procedure date up to 3 months post-procedure, after 3 months post-procedure. The month interval between index procedure and medication administration is calculated as:

(Date of medication started - Date of index procedure + 1) / (365.25/12) and rounded to 2 decimal places.

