6.3.2 Exclusion Criteria

Subjects who meet any of the following criteria are not eligible for participation in the study:

1. Patients for whom radiotherapy is contraindicated
2. Previous thoracic or abdominal radiotherapy

TraceIT Tissue Spacer (TIPS Pilot)
Protocol AGX-17-001-US
Rev. C: March 27, 2019

Page 33 of 73

3. Any GI abnormality that would interfere with the ability to access the injection site
4. Presence of tumor invasion of the duodenum detected on EUS at time of biopsy
5. Previous Whipple procedure or other resection of pancreatic tumor prior to screening
6. Active gastroduodenal ulcer or uncontrolled watery diarrhea
7. History of Chronic Renal Failure.
8. Documented history of uncontrolled diabetes (i.e., symptomatic hyperglycemia that cannot be medically managed, fasting blood glucose level above 300 mg/dL, and/or frequent swings between hyperglycemia and hypoglycemia)
9. Currently enrolled in another investigational drug or device trial that clinically interferes with this study.
10. Unable to comply with the study requirements or follow-up schedule.
11. Any condition or comorbidity that the Investigator believes would interfere with the intent of the study or would make participation not in the best interest of the subject.
12. Women who are pregnant or breast-feeding; women of child-bearing age must use contraceptives

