6.4.4 Screening/Baseline Assessments (within 45 days prior to planned TraceIT hydrogel injection)

Subjects who appear to meet the eligibility criteria will be consented for the study and will undergo screening. Information to be collected at this visit includes:

- Demographic information: date of birth, weight and height, race
- Disease documentation: tumor location, initial resectability status, tumor staging, largest pre-treatment dimension of tumor (cm)
- Medical/Surgical History/Current status: concomitant medical conditions, prior medical conditions, prior surgeries, prior therapies (e.g., induction chemotherapy)
- Physical Examination: including sitting blood pressure, pulse, temperature, weight, anticoagulation status, Zubrod Performance Score
- Laboratory testing for hematology plus platelets, creatinine, AST/ALT and bilirubin and baseline serum carbohydrate antigen (CA) 19-9
- Pregnancy test for women of child-bearing potential

- EORTC-QLQ-C30 and QLQ-PAN26
- Assessment of baseline duodenal symptoms per NCI CTCAE
- Baseline concomitant medications

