6.4.10 Final RT Fraction

The following assessments are to be performed at the final RT fraction:

- Physical Assessment (including vital signs, weight and Zubrod performance score)
- EORTC-QLQ-C30 and QLQ-PAN26
- Assessment of duodenal focused Adverse Events documented using NCI CTCAE
- Other Adverse Events per NCI CTCAE
- Changes in concomitant medications used to treat intestinal symptoms

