3.4.1 Statistical Methods

CEC adjudicated AEs will be summarized by term, by term and procedure/device relationship, and by terms and severity (CTCAE Grade). In addition to the general presentation of safety events, the following will be calculated and reported:

- The number and percentage of subjects who experienced TraceIT administration procedure-related events which result in a delay in initiation of RT
- The number and percentage of subjects with at least one duodenal adverse event presented by grade and timing; i.e., acute (within 3 months) and late (>3 months). A similar presentation will be provided for non-resected subjects only.

Additionally, the numbers and percentages will be calculated for subjects who have developed one or more following events: AEs, SAEs, UADE, SADE, procedure related

AEs, device related AEs, radiation therapy related AEs, duodenal related AEs by site and total.

Adverse event overall listing will include AE CTCAE term, AE CTCAE SOC, onset days since procedure and duration, AE attribution, CTCAE grade and adjudication term, SAE and classification, UADE, action taken, outcome and residual effects.

Single imputation will be implemented for partial start/end dates (missing month and/or day) of adverse events, or concomitant medications.

For the missing start date:

- Only the start day is missing: the 15th day of the month will be used if the resulted imputed date is after the index procedure date; otherwise the procedure date will be used.
- Both the start day and the start month are missing: the 15th day of January will be used if the resulted imputed date is after the index procedure date; otherwise the procedure date will be used.

For the missing end date:

- If the end day is missing, the 15th day of the month will be used if the resulted imputed date is after the corresponding start date; otherwise the last day of the month will be used.
- If end day and end month are both missing, the 15th day of December will be used if the resulted date is after the corresponding start date; otherwise the 31st day of December will be used.

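### SAP 5.1.5 dates changes in intestinal medication by the medication start date and ignores direction, so its period columns need not show when treatment changed or which way

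*SAP*

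**What the plan says.** The protocol records "Baseline concomitant medications" at screening (Protocol 6.4.4). At the visits after the index procedure it records "Changes in concomitant medications used to treat intestinal symptoms" (Protocol 6.4.10; the same item is in 6.4.7, 6.4.11, 6.4.12, 6.4.14 and 6.4.15).

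SAP 5.1.5 turns this into a count and percentage of ITT subjects "with any medication changes to treat intestinal symptoms will be summarized by the timing of start administration". Timing is "categorized as prior index procedure date, from index procedure date up to 3 months post-procedure, after 3 months post-procedure". The interval in months is "Date of medication started - Date of index procedure + 1) / (365.25/12) and rounded to 2 decimal places", with the bracket opening before the first date.

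SAP 3.4.1 adds: "Single imputation will be implemented for partial start/end dates (missing month and/or day) of adverse events, or concomitant medications". If a start date lacks just its day, the text runs: "the 15th day of the month will be used if the resulted imputed date is after the index procedure date; otherwise the procedure date will"; that is, the procedure date is the fallback. When day and month are both missing, 15 January is tried first, with the same fallback to the procedure date.

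Neither document says whether a dose change stays on the existing medication record or opens a new one with its own start date.

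**The concern.** The table counts changes but dates them by something else. The start of a medication and a change to it coincide only when the change is a new start. For an increase, a reduction or a stop they can be months apart, and 5.1.5 uses neither a change date nor the end date, although SAP 3.4.1 shows that end dates are held. Nor does it separate more treatment from less, which have opposite meanings for intestinal symptoms.

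Subjects already taking intestinal drugs can be enrolled. The relevant exclusion is "Active gastroduodenal ulcer or uncontrolled watery diarrhea" (Protocol 6.3.2), and the Rev C entry for that criterion gives chemotherapy-related diarrhea at screening as the reason for its wording. So drugs started before the procedure and adjusted after it are a realistic case.

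This is the only summary table of concomitant medication that the SAP specifies. At stake is whether its post-procedure columns can be read as change in treated intestinal symptoms after the spacer and radiotherapy.

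**Working it through.** The plan states no figure for this table, so there is nothing to reproduce. The check applies the SAP rules to example records.

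**Inputs.** Month formula and periods: SAP 5.1.5. Partial-date rule: SAP 3.4.1. Planned subjects: 6 (SAP 3.1.2). Assumptions: index date 1 June 2019; pre-procedure means a start date before the index date.

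**Formula.** Month = (start date − index date + 1) / (365.25/12), where 365.25/12 = 30.4375.

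**1. Baseline drug started on day −30, increased on day 60.**
- One record per drug, dated by drug start: (−30 + 1)/30.4375 = −0.95. Filed as pre-procedure.
- Dated by the change, or by a new record opened at the change: (60 + 1)/30.4375 = 2.00. Filed as index to 3 months.

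**2. The same drug reduced on day 60.**
- One record per drug: −0.95, pre-procedure, indistinguishable from the increase in step 1.
- New record: 2.00, index to 3 months, counted together with increases.

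**3. Drug started on day 20 and stopped in month 5.** A stop opens no new record, so the only date available to the formula is the start: (20 + 1)/30.4375 = 0.69, index to 3 months. The stop in the later period leaves no trace there.

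**4. Baseline drug, unchanged, with a partial start date.**

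| Recorded start | First imputation | After index? | Date used | Month |
|---|---|---|---|---|
| 2018 | 15 Jan 2018 | no | 1 June 2019 | 0.03 |
| 2019 | 15 Jan 2019 | no | 1 June 2019 | 0.03 |
| April 2019 | 15 Apr 2019 | no | 1 June 2019 | 0.03 |
| May 2019 | 15 May 2019 | no | 1 June 2019 | 0.03 |

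Here 0.03 = (0 + 1)/30.4375. All four would be classed as index to 3 months. The 2018, April and May entries certainly began before the procedure; the 2019 entry did so because it is taken to be on the baseline record. The fallback suits adverse events, which are collected only from fiducial placement onward (Protocol 9.1.1). It does not suit medications that were already in use.

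**Putting the cases together.** One record per drug fails on timing (step 1). A new record per change fails on direction (step 2). Stops are misdated under both (step 3). Imputation pushes the other way from step 1 (step 4).

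**Size.** With 6 subjects, one misplaced subject is 1/6 = 16.7 points, two are 2/6 = 33.3 and three are 3/6 = 50.0. The documents give no rate of baseline use or of later dose changes, so the number affected is unknown and may be zero.

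**The case against.** The strongest reply is that a data convention missing from the documents is being read as a defect. The SAP refers to the date a medication was started, not first started. If the CRF opens a new record at each dose change, an increase is dated correctly. That stands. A reader might infer that intensified treatment of a baseline drug is always filed as pre-procedure; the documents support this only for a single record per drug with a complete start date.

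A reader might also infer a bias toward showing no effect. That is not supported either, because the SAP 3.4.1 fallback can add unchanged baseline drugs to the first post-procedure column.

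It can further be said that the timing and direction complaints cannot both spoil the post-procedure columns: if everything is dated by original start, reductions of baseline drugs also land in the pre-procedure column. This is largely right for changes to baseline drugs. The two faults belong to different record conventions. The table is unsound under each, but for a different reason.

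It would also be too strong to say that worsening symptoms would go unseen. An adverse event includes one that has worsened (Protocol 9.1), acute intestinal events of CTCAE grade 2 or more must be documented (Protocol 9.1.1), duodenal events are reported by grade and timing (SAP 3.4.1), the quality-of-life symptom scales are compared with baseline (SAP 3.3.1), and subject listings are planned (SAP 3). With six subjects a reader can inspect each line. These sources limit the harm but do not make the table correct. Its listed prompt for further adverse-event questioning is a new medication or an unscheduled visit (Protocol 9.1.1), not an increase in an existing drug.

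Finally, eligibility is narrower than a bar on uncontrolled diarrhea alone: active ulcer, interfering GI abnormality and interfering comorbidity are also excluded. Controlled symptoms on treatment remain eligible.

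**Conclusion.** The point holds in a limited form. SAP 5.1.5 dates changes by medication start and gives no direction, which makes it a poor measure of post-procedure change under either plausible record convention. Partial-date imputation adds an error that can run the opposite way, so neither the sign nor the total size of the error can be stated.

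Each affected subject moves a column by 16.7 percentage points. This assumes six ITT subjects; the number affected depends on the CRF convention, the completeness of start dates and how many subjects take intestinal drugs at baseline, none of which the documents give. The table is descriptive, no endpoint rests on it, and other outputs cover the same symptoms. It is worth correcting because the remedy is cheap, not because a main conclusion depends on it.

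**What to change.** Amend SAP 5.1.5 to:

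- assign each change to a period by the date of the change, or by the visit date if no change date was recorded;
- report, per period, subjects with a new start or a dose or frequency increase separately from subjects with a stop or decrease;
- show baseline use as a separate reference column;
- state whether a dose change continues the existing record or opens a new one.

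Amend SAP 3.4.1 so that a medication known to predate the index procedure, from its partial date or from the baseline record, is not imputed to the procedure date.

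The cost is SAP wording and some table programming. Changes are already collected at each visit, so no new visit or assessment is needed. The small downside is that a change date must be available or the visit date used instead. The visit date is coarser: the Month 3 window is ±14 days, and the formula's cut falls between day 90 (91/30.4375 = 2.99) and day 91 (92/30.4375 = 3.02), so a change dated by that visit could land on either side. A footnote giving the number of changes dated by visit would make this visible.
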